#### 4. STATISTICAL AND ANALYTICAL PLANS

##### 4.1 General Methodology

The SMART Five Plus Year Follow-up Study analysis will be performed when all US SMART treatment arm subjects have been approached to participate in the study, and all subjects who consented to participate, have completed their 5+ year follow-up study visit.

	CD_3012_Rev B Five-Plus Year Follow-Up of SMART Trial Statistical Analysis Plan	Date Effective: November 5, 2019 Page 9 of 21
---	---	---

The number of subjects in the analysis and reasons for withdrawal will be summarized in a CONSORT flowchart. All subjects consenting to participate in the long term follow-up study will be reported as observed. No imputations are planned for missing data.

All statistical processing will be performed by Technomics Research LLC. The standard operating procedures (SOPs) of Tehcnomics Research LLC will be followed in the creation and quality control of all data displays and analyses. Analyses will be conducted using SAS® software Version 9.3 or later unless otherwise stated.

Statistical tests will be two-sided and will be performed at the 0.05 level of significance.

Descriptive statistics will be used for secondary endpoints and will include the number and percentage of subjects in each category. For continuous parameters, descriptive statistics will include n (number of subjects), mean, SD, median, minimum, and maximum. Appropriate inferential statistics will be used for the primary and secondary efficacy variables.

#### **4.2 Baseline Definition**

Intra-subject comparisons of baseline to 5+ years post procedure will be made unless otherwise stated. Baseline is defined as the last non-missing assessment at or before the baseline visit and prior to Intracept treatment.

#### **4.3 Adjustments for Covariates**

Baseline ODI score will be a covariate for the primary efficacy endpoint. The respective baseline value will be used as covariate in the secondary efficacy endpoints for VAS. No other planned analyses will include covariates.

#### **4.4 Analyses and Data Monitoring**

##### **4.4.1 Demographic and Other Baseline Characteristics**

Demographic and baseline characteristics responses will be summarized with descriptive statistics for the observed study population. A comparison of baseline demographics, co-morbidities, medical history and baseline values for ODI and VAS of the observed study population will be performed to the SMART trial full treatment arm group.

Additionally, ODI, VAS and AE histories will be compared to demonstrate that the LTFU subjects are missing at random and are not systematically different from the retained subjects.

	CD_3012_Rev B Five-Plus Year Follow-Up of SMART Trial Statistical Analysis Plan	Date Effective: November 5, 2019  Page 10 of 21
---	--	---

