### 2.3 Study Population

All US subjects that were randomized to the treatment arm of the original SMART Trial will be approached to participate in the long term (5 + year) follow-up study. A single study visit will be performed by an independent nurse CRA to collect the data.

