## 5. APPENDIX A – ANALYSIS TABLES

Table 1 - Summary of Screening (Enrolled Subjects)	
	SMART 5+ Year US Treatment Arm Cohort (N=132)
Enrolled (Consented)	% (n/N)
Study Non-Participation Reason	% (n/N)
Declined Participation	% (n/N)
Subject Withdraw Consent	% (n/N)
LTFU	% (n/N)
Death	% (n/N)
Other	% (n/N)

Table 2 - Demographic Information			
Characteristic	SMART Treated Subjects in 5+ Yr Follow-up N = XX	SMART Treated Subjects Not in 5+ Year Follow-up N = XX	t-test of Means or Exact Test of Proportions
Age (years)	Mean + SD, Median, Range	Mean + SD, Median, Range	
Gender:			
Male	% (n/N)	% (n/N)	
Female	% (n/N)	% (n/N)	

Table 3 – Baseline Social/Socioeconomic/Work History			
Characteristic	SMART Treated Subjects in 5+ Yr Follow-up N = XX	SMART Treated Subjects Not in 5+ Year Follow-up N = XX	t-test of Means or Exact Test of Proportions
Baseline Working Status			
Working	% (n/N)	% (n/N)	
Working Full-Time	% (n/N)	% (n/N)	
Working Part-Time	% (n/N)	% (n/N)	
Not Working	% (n/N)	% (n/N)	
Short-Term Disability	% (n/N)	% (n/N)	
Not Working Due to Back Pain	% (n/N)	% (n/N)	
Unemployed	% (n/N)	% (n/N)	
Retired	% (n/N)	% (n/N)	
Other	% (n/N)	% (n/N)	
Time since last worked (for subject not working due to back pain)	Mean + SD, Median, Range	Mean + SD, Median, Range	

	CD_3012_Rev B Five-Plus Year Follow-Up of SMART Trial Statistical Analysis Plan	Date Effective: November 5, 2019 Page 13 of 21
---	---	--

Table 4 – Baseline Characteristics			
Characteristic	SMART Treated Subjects in 5+ Yr Follow-up N = XX	SMART Treated Subjects Not in 5+ Year Follow-up N = XX	t-test of Means
Baseline ODI	Mean + SD, Median, Range	Mean + SD, Median, Range	
Baseline VAS	Mean + SD, Median, Range	Mean + SD, Median, Range	

Table 5 – Baseline Low Back Pain History			
Characteristic	SMART Treated Subjects in 5+ Yr Follow-up N = XX	SMART Treated Subjects Not in 5+ Year Follow-up N = XX	t-test of Means or Exact Test of Proportions
Length of Time Experience LBP			
< 6 months	% (n/N)	% (n/N)	
6 months to < 1 year	% (n/N)	% (n/N)	
1 year to < 2 years	% (n/N)	% (n/N)	
2 years to < 3 years	% (n/N)	% (n/N)	
3 years to < 5 years	% (n/N)	% (n/N)	
> 5 years	% (n/N)	% (n/N)	
# of days a Week Subject Experiences Low Back Pain	Mean + SD, Median, Range	Mean + SD, Median, Range	
Modic Type by Level & Endplate			
L3 Superior Endplate	% (n/N)	% (n/N)	
Modic I	% (n/N)	% (n/N)	
Modic II	% (n/N)	% (n/N)	
L3 Inferior Endplate	% (n/N)	% (n/N)	
Modic I	% (n/N)	% (n/N)	

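### SAP 4.4.1 compares attendees with the full treatment arm that contains them, which shrinks any attendee/non-attendee difference and disagrees with the SAP's own table shells

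*SAP*

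**What the plan says.** The first paragraph of SAP 4.4.1 says that a comparison of demographics, co-morbidities, medical history and baseline ODI and VAS in the observed population "will be performed to the SMART trial full treatment arm group". It names no statistical test.

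SAP 2.3 shows where attendees come from: "All US subjects that were randomized to the treatment arm of the original SMART Trial will be approached to participate". They are therefore a subset of the comparator.

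The shells in SAP Appendix A use a different comparator. Tables 2-7 (demographics, work history, baseline ODI and VAS, low back pain history, low back treatment history, treated levels) and Table 11 (3-month SMART outcomes) put attendees beside "SMART Treated Subjects Not in 5+ Year Follow-up". The test column reads "t-test of Means or Exact Test of Proportions" in all of these except Table 4, which has only the t-test.

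The second paragraph of 4.4.1 adds a separate comparison: "ODI, VAS and AE histories will be compared to demonstrate that the LTFU subjects are missing at random". Its counterpart group is the retained subjects, so those two groups do not overlap.

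No sentence in the SAP says whether the text or the shells govern.

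**The concern.** A reader of the baseline comparison wants to know whether the people who came back resemble those who did not. Setting attendees against a group made up largely of themselves answers a weaker question, and the answer looks more reassuring the higher the participation.

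This matters because SAP 4.4.2 bases the primary analysis on consented treated subjects with a 5+ year visit, without imputation. Baseline comparability is therefore part of how readers will judge selection. A programmer working from the text would produce a different table from one working from the shells. Where an item has no shell, the text is all there is.

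**Working it through.** The documents give no expected participation, power or sample size for this comparison, so there is no planned figure to reproduce.

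**Inputs from the documents.** US treatment arm N = 133 (SAP 2.1; the Table 1 shell says 132, which changes the results below very little). Two-sided 0.05 level (SAP 4.1).

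**Assumptions.** Participation f from 50% to 90%. A true attendee/non-attendee gap of 0.5 SD, shown as 5 points with SD 10. Full arm taken to mean the US arm.

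**Step 1: dilution.** Let A and B be the attendee and non-attendee means.

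Full-arm mean = f·A + (1 - f)·B, so A - full-arm mean = (1 - f)·(A - B).

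This is an identity. It holds whatever test is used, or if none is.

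**Step 2: what happens if the shells' independent-group tests are applied to overlapping groups.** With n = fN attendees, the independent-groups formula gives variance σ²(1/n + 1/N) = σ²(1 + f)/(fN). The true variance of A - full-arm mean is (1 - f)²σ²[1/(fN) + 1/((1 - f)N)] = σ²(1 - f)/(fN). The naive z is therefore √[(1 - f)/(1 + f)] times the z of the disjoint comparison.

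**Step 3: numbers (N = 133, normal approximation).**

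| Assumed f | In / not in | Factor (1 - f) | 5-point gap shows as | z ratio | Power, disjoint | Power, overlapping | Real type I error, overlapping |
|---|---|---|---|---|---|---|---|
| 50% | 66 / 67 | 0.504 | 2.52 | 0.58 | 82% | 31% | 0.0007 |
| 60% | 80 / 53 | 0.398 | 1.99 | 0.50 | 81% | 13% | 0.00009 |
| 75% | 100 / 33 | 0.248 | 1.24 | 0.38 | 70% | 0.3% | 0.0000002 |
| 90% | 120 / 13 | 0.098 | 0.49 | 0.23 | 40% | about 0% | about 0 |

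A 10,000-run simulation at 100/33 agrees: power 70% disjoint against 0.2% overlapping, and type I error 4.8% against no rejections.

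**Step 4: one worked case (assumed 8-point gap, SD 16, 100/33 split).**

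- Disjoint: 8 / [16·√(1/100 + 1/33)] = 2.49, p = 0.014.
- Overlapping, treated as independent: 8·(33/133) / [16·√(1/100 + 1/133)] = 0.94, p = 0.35.

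**Step 5: which items depend on the text alone.**

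| Item named in 4.4.1 | Disjoint shell? |
|---|---|
| Demographics | Yes, Table 2 (work history in Table 3) |
| Baseline ODI and VAS | Yes, Table 4 |
| Medical history: low back | Yes, Tables 5 and 6 |
| Medical history: other | No |
| Co-morbidities | No |
| ODI and VAS histories | Table 11 for 3-month change; text already says lost versus retained |
| AE histories | No shell, but text already says lost versus retained |

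**The case against.** The strongest reply is that this is a loose phrase which the rest of the SAP corrects. Most of that stands. Every shell that carries a between-group test uses disjoint groups, and Table 11 covers early outcome, which bears more directly on outcome-related dropout than demographics do. If the shells are followed, the delivered tables are right for most items.

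Three stronger readings are tempting, and the documents do not support them.

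- *The planned t-tests are invalid.* The full-arm sentence names no test, and the shells' tests are attached to disjoint groups. The power, type I error and p-value figures for overlapping groups describe what would follow if the two were combined, which neither place prescribes. A variance that allows for the overlap would recover the disjoint z.
- *This comparison is the plan's evidence that loss to follow-up does no harm.* That purpose is stated only in the next paragraph, which sets out to show that "the LTFU subjects are missing at random and are not systematically different from the retained subjects". That comparison is already disjoint. The full-arm sentence states no missing-data purpose and can be read as describing representativeness.
- *The AE comparison has the same defect.* It does not. It lacks a shell, which is a separate matter.

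It is also fair to say that the full arm may not mean the US arm. SMART enrolled 23 subjects in Europe (SAP section 1), and treated Europeans were never eligible for this follow-up. The factor would then differ, and region would be mixed with attrition.

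What the reply does not remove is that the text prescribes a different comparator from the shells, with no rule for choosing, and that at least two listed items have only the text to go by.

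**Conclusion.** The point holds as a conflict between the text and the shells, with a real but limited consequence. The comparator in 4.4.1 contains the attendees, and using it reduces any displayed attendee/non-attendee difference to (1 - participation) of its size: 40%, 25% or 10% at assumed participation of 60%, 75% or 90%. That rests on arithmetic and on reading the full arm as the US arm. Only if independent-group tests were also run on the overlapping groups would they become very conservative, with power of 0.3% instead of 70% at 75% participation and a 0.5 SD gap.

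The items exposed, because no shell overrides the text, are mainly co-morbidities and medical history outside the low back. A reader might infer that the primary ODI analysis is compromised. It is not affected, since SAP 4.4.2 does not use this comparison.

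**What to change.** In the first paragraph of SAP 4.4.1, replace the full-treatment-arm comparator with *US SMART treated subjects not in the 5+ year follow-up*, and state that it applies to every item listed there, including co-morbidities and medical history. Text and shells then agree, and the question of whether European subjects belong in the comparator disappears. Adding rows for co-morbidities and other medical history to an existing shell would be a useful but optional complement.

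The cost is one sentence of SAP wording. The comparison concerns baseline data from SMART, so it needs no further subject contact. The downside is that displayed differences may look larger than they would against the full arm.

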##### **4.4.3.3 Regression to the Mean**

Regression to the mean analyses for ODI and VAS will be performed as supplemental analyses. See Appendix A - Table 11.

 relevant medsystems	CD_3012_Rev B  Five-Plus Year Follow-Up of SMART Trial Statistical Analysis Plan	Date Effective: November 5, 2019  Page 11 of 21
---	---	--

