**5+ Year Follow-up Study Endpoints:**

Tables 8 and 9 will be performed for both the ITT (as treated) population and the Intracept treated only population.

Table 8 – Primary Endpoint Results	
	SMART 5+ Yr Follow-up Subjects N = XX Mean ± SD (N), Median [Interquartile Range], Range or % (n/N)
Time of Assessment	
Years since Index Procedure	Mean + SD, Median, Range
Percent with at Least 5 years of Follow-up	% (n/N)
ODI	(N=XX)
Baseline ODI Score (Mean + SD, Median, Range)	Mean + SD, Median, Range
5+ Year ODI Score (Mean + SD, Median, Range)	Mean + SD, Median, Range
Mean change in ODI score from baseline to 5+ Years post-treatment	Mean + SD, Median, Range ( p-value )
ODI Responder Rates	
Subjects with ≥ 10-point ODI decrease	% (n/N) ( p-value )
Subjects with ≥ 15-point ODI decrease	% (n/N) ( p-value )
Subjects with ≥ 20-point ODI decrease	% (n/N) ( p-value )
ODI Response Quartiles	
Subjects with ≤ 24% or less decrease	% (n/N)
Subjects with 25-49% decrease	% (n/N)
Subjects with 50-74% decrease	% (n/N)
Subjects with 75-100% decrease	% (n/N)
	(p-value)

	CD_3012_Rev B Five-Plus Year Follow-Up of SMART Trial Statistical Analysis Plan	Date Effective: November 5, 2019 Page 16 of 21
---	--	---

Table 9 – Secondary Endpoints Results	
	SMART 5+ Yr Follow-up Subjects N = XX
10 Point VAS Numeric Pain Scale	
Baseline VAS Score (Mean + SD, Median, Range)	Mean + SD, Median, Range
5+ Year VAS Score (Mean + SD, Median, Range)	Mean + SD, Median, Range
Mean change in VAS score from baseline to 3 months post-treatment	Mean + SD, Median, Range ( p-value )
VAS Responder Rates	
% of subjects with $\geq$ 1.5 Pt VAS decrease	% (n/N) ( p-value )
% of subjects with $\geq$ 2.0 Pt VAS decrease	% (n/N) ( p-value )
VAS Response Quartiles	
Subjects with $\leq$ 24% or less decrease	% (n/N)
Subjects with 25-49% decrease	% (n/N)
Subjects with 50-74% decrease	% (n/N)
Subjects with 75-100% decrease	% (n/N)
	( p-value )

Table 10 – Regression to the Mean Analysis	
	SMART 5+ Yr Follow-up Subjects N = XX
Regression to the Mean	
Average change in ODI in CONTROL group between baseline and 1 year	Mean, N, 95% CI, t-test p (Ho: $\delta=0$ )
Average change in ODI in CONTROL group between baseline and 2 years	Mean, N, 95% CI, t-test p (Ho: $\delta=0$ )

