Average change in ODI in INTRACEPT group between baseline and 1 year	Mean, N, 95% CI, t-test p (Ho: $\delta=0$ )
Average change in ODI in INTRACEPT group between baseline and 2 years	Mean, N, 95% CI, t-test p (Ho: $\delta=0$ )
Average change in ODI in INTRACEPT group between baseline and 5+ years	Mean, N, 95% CI, rm F-test p (Ho: $\delta=0$ )
Time (per year) effect on ODI in INTRACEPT group	Mean, N, 95% CI, rm F-test p (Ho: time=0)
Average change in VAS in CONTROL group between baseline and 1 year	Mean, N, 95% CI, t-test p (Ho: $\delta=0$ )
Average change in VAS in CONTROL group between baseline and 2 years	Mean, N, 95% CI, t-test p (Ho: $\delta=0$ )
Average change in VAS in INTRACEPT group between baseline and 1 year	Mean, N, 95% CI, t-test p (Ho: $\delta=0$ )
Average change in VAS in INTRACEPT group between baseline and 2 years	Mean, N, 95% CI, t-test p (Ho: $\delta=0$ )
Average change in VAS in INTRACEPT group between baseline and 5+ years	Mean, N, 95% CI, t-test p (Ho: $\delta=0$ )
Time (per year) effect on VAS in INTRACEPT group	Mean, N, 95% CI, rm F-test p (Ho: time=0)

	CD_3012_Rev B Five-Plus Year Follow-Up of SMART Trial Statistical Analysis Plan	Date Effective: November 5, 2019 Page 17 of 21
---	--	---

Table 11 – Comparison of SMART Endpoints			
Characteristic	SMART Treated Subjects in 5+ Yr Follow-up N = XX	SMART Treated Subjects Not in 5+ Year Follow-up N = XX	t-test of Means or Exact Test of Proportions
Change in ODI (Baseline to 3 Months)	Mean + SD, Median, Range	Mean + SD, Median, Range	
Change in VAS (Baseline to 3 Months)	Mean + SD, Median, Range	Mean + SD, Median, Range	
ODI Responders ( $\geq$ point ODI reduction)	% (n/N)	% (n/N)	

Table 12 – Opioids & Injections Utilization	
SMART 5+ Yr Follow-up Subjects N = XX	
Opioid Use	
Subjects Taking Opioids at Baseline	% (n/N)
Subjects actively taking Opioids in last 30 days (5+ Year Follow-up Visit)	% (n/N)
Opioid Dosage (in subjects taking opioids)	
Opioid Dosage at Baseline	Mean + SD, Median, Range
Opioid Dosage at 5+ years post treatment	Mean + SD, Median, Range
Epidural Injections	
Subjects with prior injections at baseline	Mean + SD, Median, Range
Subjects with injections in 12 months prior to 5+ year post treatment visit	Mean + SD, Median, Range
Subjects with injections for low back pain treatment in the same location as Intracept treatment (in the past 12 months):	Mean + SD, Median, Range

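### SAP 4.4.1 sets out to demonstrate that losses are missing at random, which observed data cannot do, and no missing-data sensitivity analysis is specified for the returner-only estimate

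*SAP*

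**What the plan says.** SAP 2.3 sets the target group: "All US subjects that were randomized to the treatment arm of the original SMART Trial will be approached to participate". SAP 4.1 then says "All subjects consenting to participate in the long term follow-up study will be reported as observed". Sections 4.1, 4.4.2 and 4.4.3, and Protocol 6.1, rule out imputation. The efficacy set in 4.4.2 is consented treated subjects who have a 5+ year visit. Under 4.3 the only covariate is the baseline score. Section 4.4.2 attaches a durability conclusion to a primary p-value of 0.05 or less.

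On those who do not return, 4.4.1 says "ODI, VAS and AE histories will be compared to demonstrate that the LTFU subjects are missing at random and are not systematically different"; the comparison group is those who stayed in follow-up. The supporting outputs are:

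- **Table 1:** reasons for non-participation.
- **Tables 2 to 7:** baseline and treatment data, returners against non-returners.
- **Table 11:** the only outcome table by return status. Its rows are "Change in ODI (Baseline to 3 Months"), the same for VAS, and an ODI responder row with no visit shown. It has no 12- or 24-month rows and no AE row.
- **Table 10:** repeated-measures F-tests for "Average change in ODI in INTRACEPT group between baseline and 5+ years" and "Time (per year) effect on ODI in INTRACEPT group", with a yearly time effect for VAS as well. Section 4.4.3.3 gives its purpose: "Regression to the mean analyses for ODI and VAS will be performed as supplemental analyses. See Appendix A - Table 11". That cites the wrong table number.

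**The concern.** Missing at random means that, given the observed data, the chance of being missing does not depend on the unobserved 5+ year score. Observed histories can make this more or less plausible but cannot demonstrate it. The sentence also merges two ideas. A difference in observed history argues against missing completely at random, not against missing at random. And because the conclusion is written in advance, a non-significant Table 11 could be reported as proof that loss was random.

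If people who did poorly are less likely to return, the returner-only mean and responder rates are too high. The plan then offers no second 5+ year estimate against which to judge them.

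**Working it through.** The documents give no retention, SD or power for this study, so there is no stated figure to reproduce. Retention, correlations and return mechanisms below are assumptions.

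**1. Does Table 10 fill the gap?** Its column is headed for 5+ year follow-up subjects, yet it holds rows such as "Average change in ODI in CONTROL group between baseline and 1 year". Control subjects are not approached under SAP 2.3, so the header cannot be read literally and the population of the Intracept rows is unclear. No model or visit list is given. The 5+ year change is tested by repeated-measures F-test for ODI and by t-test for VAS. Nothing is split by return status. As written it is not a missing-data analysis.

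**2. SD of ODI change.** From the 24-month results in Protocol 2 (introduced there for per-protocol subjects), assuming normality:

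- mean 23.4 with 76.4% at 10 points or more: (23.4 − 10)/0.719 = 18.6
- 57.5% at 20 points or more: (23.4 − 20)/0.189 = 18.0
- midpoint: 18.3

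**3. What the history comparison can detect.** Two-sample t-test, two-sided 0.05, 133 subjects, SD 18.3. The 95% CI half-width is 1.98 × 18.3 × √(1/n₁ + 1/n₂).

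| Return / not | Difference for 80% power | Power for 5 points | CI half-width |
|---|---|---|---|
| 90 / 43 | 0.523 × 18.3 = 9.6 | 31% | 6.7 |
| 100 / 33 | 0.567 × 18.3 = 10.4 | 27% | 7.3 |
| 110 / 23 | 0.647 × 18.3 = 11.8 | 22% | 8.3 |

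With 100 returning and SD 15 to 20, the detectable difference is 8.5 to 11.3. SAP 2.5 gives the MCID as 10 points.

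**4. Size of the bias.** Simulation of 133 subjects, 8,000 runs per scenario. ODI improvements are trivariate normal with means 20.5 (3 months), 23.4 (24 months) and 20 (5 years, assumed) and SD 18.3. Correlations are 0.55 (3 with 24 months), 0.65 (24 months with 5 years) and 0.40 (3 months with 5 years). Return depends on being a 10-point responder at 24 months or at 5 years. The adjusted estimate is a maximum-likelihood stand-in for a repeated-measures model using the 3- and 24-month changes.

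The returner-only bias has a closed form: ρ × SD × φ(z) × (a − b)/r. Here a and b are the return rates of responders and non-responders, z = (mean at the driving visit − 10)/SD, p = Φ(z) and r = p·a + (1 − p)·b. For example:

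- 24-month driver, 85/35%: z = 0.732, φ = 0.305, p = 0.768, r = 0.734; 0.65 × 18.3 × 0.305 × 0.50/0.734 = 2.5
- 5-year driver (ρ = 1), 85/35%: z = 0.546, φ = 0.344, p = 0.708, r = 0.704; 18.3 × 0.344 × 0.50/0.704 = 4.5

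| Driver | Return, responders/non-responders | Overall return r | Returner-only bias | Left after adjustment if all / half / none of the non-returners have 24-month scores |
|---|---|---|---|---|
| 24 months | 80/60% | 75% | +1.0 | 0 / +0.3 / +0.6 |
| 24 months | 85/50% | 77% | +1.6 | 0 / +0.5 / +1.1 |
| 24 months | 85/35% | 73% | +2.5 | 0 / +0.7 / +1.7 |
| 5 years | 80/60% | 74% | +1.7 | +1.0 / +1.2 / +1.4 |
| 5 years | 85/50% | 75% | +2.9 | +1.8 / +2.1 / +2.5 |
| 5 years | 85/35% | 70% | +4.5 | +2.8 / +3.3 / +3.9 |

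With the 24-month driver:

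- The 10-point responder rate among returners is 73.0, 74.5 and 76.3%, against a true 70.8%.
- The 3-month test flags a difference in 15, 37 and 60% of runs.
- A 24-month test flags 39, 83 and 97% if all non-returners have 24-month scores, and 25, 60 and 87% if half do.

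With weaker or stronger correlations (0.40, 0.50, 0.30 to 0.70, 0.80, 0.60), returner-only bias is +0.7 to +3.1 (24-month driver) and +1.7 to +4.5 (5-year driver). The test against zero was significant in every run.

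**5. A case the check cannot see.** In a separate simulation (SD 15, 75% return, 4,000 runs), return depended only on the part of the 5-year outcome that history does not explain. The history test rejected in 4.8 to 5.5% of runs, its null rate, while the returner-only mean was 2.3 to 4.8 points too high.

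**6. Assumed-shortfall line.** If non-returners improve by δ points less than returners, the arm-wide mean falls by (share not returning) × δ:

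- 90 return: 43/133 × 10 = 3.2; × 20 = 6.5
- 100 return: 33/133 × 10 = 2.5; × 20 = 5.0
- 110 return: 23/133 × 10 = 1.7; × 20 = 3.5

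**The case against.** The strongest reply is that the damage is limited. The study is a single telephone visit, most secondary results are descriptive, and the plan already discloses subject flow, reasons for non-participation and returner against non-returner tables. The primary test survives every scenario, and when history drives return the bias is 1.0 to 2.5 points against an assumed mean of 20. This is fair, and it sets the severity. It does not rescue a sentence that promises a demonstration the data cannot give.

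The magnitudes do rest on assumptions. If 120 of 133 return, a 10-point shortfall costs only 13/133 × 10 = 1.0 point. The history check is then weaker still: its half-width is 1.98 × 18.3 × √(1/120 + 1/13) = 10.6 points. The recovery figures would also change if Table 10's yearly time effect means a model linear in time.

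The control rows cover only years 1 and 2 of the original trial, so they need no new contact and may reflect a template fault. That is plausible, but it leaves the population of the Intracept rows undefined.

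Two further points stand. Section 4.4.1 speaks of LTFU subjects, whereas Table 1 lists LTFU separately from declined, withdrawn, death and other. It also compares returners with the full treatment arm, while the tables compare them with non-returners. Both can be settled in the same edit.

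**Conclusion.** The concern holds. The stated purpose of the comparison in 4.4.1 cannot be met by any observed data, and no planned output is specified as a missing-data sensitivity analysis. With 90 to 110 of 133 returning and SD 18.3, the check would reliably detect only ODI differences of about 10 to 12 points. Under the main simulated mechanisms the returner-only mean is 1.0 to 4.5 points too high. For scale, the original treatment-sham difference was 20.5 − 15.2 = 5.3 points.

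The test against zero is not threatened. What is exposed is the size of the mean change, the responder rates and the durability statement in 4.4.2. The sponsor should make the change. Confidence in the logical point is high. Confidence in the magnitudes is moderate, because retention, correlations, the 5-year mean and the return mechanism are all assumed.

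**What to change.** First:

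- **(a)** In 4.4.1, drop the claim to demonstrate missing at random and the absence of systematic difference. Say instead that differences between returning and non-returning subjects will be described, with 95% CIs, and define which non-participants are included.
- **(b)** In Table 11, add 12- and 24-month ODI and VAS changes and AE rows, and state the visit for the responder row. Its threshold is also absent from the text available here, possibly an extraction fault, and should be confirmed.

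Then, as supporting analyses:

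- **(c)** Specify the Table 10 repeated-measures model, for ODI and VAS alike, on all US treated subjects, using available SMART visits plus the 5+ year visit. Report its 5+ year mean beside the observed-data result as a sensitivity analysis. State that it is valid only if return depends on observed data and that it recovers less if 24-month data are incomplete. State how deaths are handled and which denominator applies (133 in SAP 2.1, 132 in Table 1). Correct the cross-reference in 4.4.3.3 to Table 10.
- **(d)** Add one line for a range of δ: arm-wide mean = returner mean − (share not returning × δ). Label it an assumed scenario, outside the no-imputation analysis required by the SAP and Protocol 6.1.

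The cost of (a) and (b) is wording and a few table rows. Item (c) needs a proper model specification and modest programming. Item (d) is arithmetic. The downside is supporting figures that may be less favourable. The documents do not say how complete the 24-month data are. If return depends on the 5-year outcome, (c) removes only part of the bias: in the main simulation about 40% with complete 24-month data and about 30% with half (roughly 17% to 53% across the correlations tried).
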